^u Investigational product (AMG 570 or placebo) will be administered as described in Section 7.1.1. Subjects will be observed for at least 30 minutes at the site or by the home health care provider following investigational product administration.

Table 2-2. Schedule of Activities – Safety Follow-up Period^a

Safety Follow-up Week ± Visit Window	4 Weeks ± 5 days after last IP dose	4 Weeks ± 5 days after prior safety follow-up visit	4 Weeks ± 5 days after prior safety follow-up visit	4 Weeks ± 5 days after prior safety follow-up visit EOS
GENERAL AND SAFETY ASSESSMENTS				
Vital signs	X	X	X	X
Adverse events	X	X	X	X
Serious adverse events ^b	X	X	X	X
Concomitant medications review	X	X	X	X
LABORATORY ASSESSMENTS				
Urine pregnancy test	X	X		
Hematology		X		X
Hepatitis B and C ^c			X	
IMMUNOGENICITY				
PHARMACOKINETIC ASSESSMENTS				
Pharmacokinetic Samples	X	X	X	X

EOS = end of study; IP = investigational product; PCR = polymerase chain reaction

^a This table applies for subjects who have completed the planned 52-week treatment period. Subjects are required to attend as many follow-up visits as necessary to ensure a minimum of 16 weeks of safety follow-up after the last administration of the investigational product.

^b After end of study, serious adverse events suspected to be related to investigational product will be reported to Amgen. Please refer to Section 9.2.3.1.1.3 for additional details.

[figure not shown]
^c For subjects who require monitoring, PCR test to assess viral load should be performed at approximately every 3 months from baseline and up to a minimum of 16 weeks after the last administration of the investigational product. See Section 6.2 criterion 208.

Product: Rozibafusp Alfa (AMG 570)

Protocol Number: 20170588

Date: 24 May 2022

Page 26 of 121

Product: Rozibafusp Alfa (AMG 570)

Protocol Number: 20170588

Date: 24 May 2022

Page 27 of 121

3. Introduction

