5.1 Overall Design

This is a Bayesian adaptive phase 2b, multi-center, double-blind, randomized, placebo-controlled, 52-week, dose-ranging study in subjects with active SLE and inadequate response to SOC therapies including **oral corticosteroids (OCS)**, immunosuppressants, and immunomodulators. Previous biologic use is allowed with an adequate washout period (see Exclusion Criterion 215).

Approximately 320 subjects will be enrolled and randomized to receive AMG 570 SC at 70 mg Q2W, 280 mg Q2W, 420 mg Q2W, or placebo. The randomization starts as 1:1:1:1 and then could be adapted at each interim analysis (IA) (if before full enrollment) based on the clinical efficacy (Response Adaptive Randomization [RAR]) for allocating more subjects to more efficacious doses and fewer subjects to less efficacious doses. The randomization allocation probability for placebo group will be kept constant at 25%. Randomization will be stratified by geographic region (North America + Western Europe vs rest of the world [ROW]) and screening **Hybrid Systemic Lupus Erythematosus Disease Activity Index (hSLEDAI)** score (≥ 10 or < 10).

Study duration for a single subject will be 52 weeks (treatment period) plus the screening period and safety follow-up period. Investigational product will be administered Q2W with the final dose at week 50. If a subject discontinues investigational product prior to completing week 52 visit, the subject will be encouraged to continue in the study and maintain the planned scheduled assessment for monthly efficacy and safety visits **through week 52 (Table 2-1)**. **Subjects are required to attend as many follow-up visits as necessary to ensure a minimum of 16 weeks of safety follow-up after the last administration of the investigational product. For subjects who discontinue investigational product prior to week 36, the safety follow-up visits will be included within the 52-week period and no additional safety follow-up visits will be required.** Immunogenicity [REDACTED] and PK samples should be collected at the first 4 visits after investigational product discontinuation.

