- Decreased washout period for Janus kinase (JAK) inhibitor from 3 to 1 month prior to screening based on information available for the pharmacokinetic/pharmacodynamic profile of these drugs (criterion 213).
- Clarify criterion 215 by adding immunosuppressive or immunomodulatory activity to treatment with a biologic agent, reduce washout period for abatacept to

3 months prior to screening based on its pharmacokinetic/pharmacodynamic profile, and clarify that pharmacodynamic activity of other biologics at screening should be considered when evaluating washout periods.

- Clarify the timeframe within which a subject must not plan to receive a live vaccine (criterion 217).

Prior/Concurrent Clinical Study Experience:

- Revise washout period for treatment with an investigational product or device to consider the pharmacokinetic and pharmacodynamic profile of those products at screening (criterion 219).

Diagnostic Assessments:

- Include Gilbert's Syndrome as an exception for presence of laboratory abnormalities during screening in serum total bilirubin since these patients present non clinically relevant elevated bilirubin levels (criterion 221).

Other Exclusions was updated to:

[figure not shown]
- Clarify that serum pregnancy test is required at screening and urine pregnancy test is required at day 1 visit (criterion 225).

15. Schedule of Activities-Safety Follow-up Period was updated to (Table 2-2):

- Clarify that this table applies for the subset of subjects that completed the planned 52-week treatment period and emphasize that subjects are required to attend as many visits as necessary to ensure a minimum of 16 weeks of safety follow-up after last dose of the investigational product.
- Clarify that safety follow-up visits should be scheduled in relation to last administration of the investigational product and not visit week 52.
- Add frequency for monitoring viral load to evaluate hepatitis B and C.
- Remove urine pregnancy tests from the last two safety follow-up visits.

16. Minor updates were included in the footnotes of the Schedule of Activities Treatment Period to clarify information regarding starting time of home health care visits, the option of conducting a QuantiFERON-TB test locally, assessment frequency of serum viral DNA and RNA for hepatitis B and C, and [REDACTED]. Additionally, for clarity purposes details no longer relevant to the assessments were removed (Table 2-1 footnotes e, f, g, i, q, and r).

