5.2 Study Points of Reference

Baseline

Baseline is defined as the closest recorded measurements prior to or on the first dose of study treatment for subjects receiving study treatment regardless of time collected. For subjects not receiving treatment, baseline is defined as the closest recorded measurements prior to or on the enrollment date.

Study Day 1

Study day 1 for each subject is the first day of IP administration or the day of randomization for subjects who did not receive IP.

Study Day

Study day for each subject is defined as (day of interest – study day 1) + 1 for dates on or after study day 1, or (day of interest – study day 1) for dates prior to study day 1.

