Appendix D. Analytical Windows

The last measurement for the endpoint of interest taken prior to or on the first dose of IP in this study, unless stated otherwise, will be defined as a baseline visit and the analysis visit name will be 'Baseline'. For any visit up to Day 1 pre-dose which is not a baseline visit, the analysis visit will be 'Pre-analysis'.

Since the actual visit for a subject may not exactly coincide with their scheduled visit date, to allow for variations in scheduling, the following visit windows will be used to assign evaluations to a most appropriate nominal visit for analysis and summarization. Furthermore, there will be no gaps between visit windows in order to include as many data points as possible for summarization.

If more than one actual visit (including the unscheduled visits) falls within the same defined window, the visit closest to the target day with non-missing data will be considered for analysis. If two actual visit dates are at the same distance from the target day, the latest visit with non-missing data will be considered for analysis.

The rules above for selecting a visit from multiple ones within the same visit window are not applicable to retest values of lab data. If the lab measurement is a retest, the retest value will be used.

Efficacy assessment (tender/swollen joint count, hSLEDAI, BILAG, SELENA-

SLEDAI Flare Index, PGA, CLASI), weight, and laboratory assessment [REDACTED]

[REDACTED], chemistry, urinalysis)

Study Visit	Target Day	Study Day
Baseline	1	Last evaluation prior to or on Study Day 1
Week 4	29	2 - 42
Week 8	57	43 - 70
Week 12	85	71 - 98
Week 16	113	99 - 126
Week 20	141	127 - 154
Week 24	169	155 - 182
Week 28	197	183 - 210
Week 32	225	211 - 238
Week 36	253	239 - 266
Week 40	281	267 - 294
Week 44	309	295 - 322
Week 48	337	323 - 350
Week 52	365	351 - 394

Hematology

Study Visit	Target Day	Study Day
Baseline	1	Last evaluation prior to or on Study Day 1
Week 4	29	2 - 42
Week 8	57	43 - 70
Week 12	85	71 - 98
Week 16	113	99 - 126
Week 20	141	127 - 154

Week 24	169	155 - 182
Week 28	197	183 - 210
Week 32	225	211 - 238
Week 36	253	239 - 266
Week 40	281	267 - 294
Week 44	309	295 - 322
Week 48	337	323 - 350
Week 52	365	351 - 392
Week 60	421	393 - 448
Week 68	477	≥ 449

Vital sign

Study Visit	Target Day	Study Day
Baseline	1	Last evaluation prior to or on Study Day 1
Week 2	15	2 - 21
Week 4	29	22 - 35
Week 6	43	36 - 49
Week 8	57	50 - 63
Week 10	71	64 - 77
Week 12	85	78 - 91
Week 14	99	92 - 105

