Week 16	113	106 - 119
Week 18	127	120 - 133
Week 20	141	134 - 147
Week 22	155	148 - 161
Week 24	169	162 - 175

Week 26	183	176 - 189
Week 28	197	190 - 203
Week 30	211	204 - 217
Week 32	225	218 - 231
Week 34	239	232 - 245
Week 36	253	246 - 259
Week 38	267	260 - 273
Week 40	281	274 - 287
Week 42	295	288 - 301
Week 44	309	302 - 315
Week 46	323	316 - 329
Week 48	337	330 - 343
Week 50	351	344 - 357
Week 52	365	358 - 378
Week 56	393	379 - 406
Week 60	421	407 - 434
Week 64	449	435 - 462
Week 68	477	≥ 463

, SDI

Study Visit	Target Day	Study Day
Baseline	1	Last evaluation prior to or on Study Day 1
Week 24	169	2 - 266
Week 52	365	267 - 394

Pharmacokinetic assessment

Study Visit	Target Day	Study Day
Baseline	1	Last evaluation prior to or on Study Day 1
Week 4	29	2 - 42
Week 8	57	43 - 70
Week 12	85	71 - 98
Week 16	113	99 - 126
Week 20	141	127 - 154
Week 24	169	155 - 210
Week 36	253	211 - 280
Week 44	309	281 - 336
Week 52	365	337 - 378
Week 56	393	379 - 406
Week 60	421	407 - 434
Week 64	449	435 - 462
Week 68	477	≥ 463

PROs (SF-36v2, PROMIS Fatigue SF 7A, LupusQOL, PtGA)

Study Visit	Target Day	Study Day
Baseline	1	Last evaluation prior to or on Study Day 1
Week 4	29	2 - 56
Week 12	85	57 - 98
Week 24	169	99 - 210
Week 36	253	211 - 280
Week 44	309	281 - 336
Week 52	365	337 - 394

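### SAP Appendix D counts the follow-up windows for vital signs and PK from week 52, but the protocol schedules those visits from the last dose at week 50, so each window opens on the planned visit day

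*SAP*

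**What the plan says.** Protocol section 5.1 fixes the end of dosing: "Investigational product will be administered Q2W with the final dose at week 50". Table 2-2, for subjects who complete the 52-week treatment period, times the first safety follow-up visit at "4 Weeks ± 5 days after last IP dose" and each of the next three at "4 Weeks ± 5 days after prior safety follow-up visit". Vital signs and PK samples are taken at all four. The Amendment 3 summary of changes confirms that this anchor was intended: "Clarify that safety follow-up visits should be scheduled in relation to last administration of the investigational product and not visit week 52".

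The SAP states that it details the analyses of Amendment 3. Section 5.2 sets the time origin: "Study day 1 for each subject is the first day of IP administration". In the Appendix D vital-sign table the last dosing visit reads "Week 50 351 344 - 357" and the first follow-up visit reads "Week 56 393 379 - 406". The rows that follow are Week 60 (target 421, days 407-434), Week 64 (449, 435-462) and Week 68 (477, day 463 onward). The PK table has the same four rows. Where two visits share a window, "the visit closest to the target day with non-missing data will be considered for analysis"; a tie goes to the later visit.

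**The concern.** The two documents anchor the same four visits two weeks apart. Appendix D exists to give each record its most appropriate nominal visit, which needs a target near the planned day and some margin on both sides. Here an on-time visit has no margin on the early side.

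The outputs at stake are the vital-sign summaries over time (SAP 9.6.3) and the serum-concentration summaries by sampling time point (SAP 9.7.1). If some subjects' 8-week samples carry the same label as other subjects' 4-week samples, the by-visit table after week 52 does not describe a defined time off drug. An early first follow-up record also competes with the week 52 visit for a single place in the Week 52 column.

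**Working it through.** **1. Reproduce the SAP targets.** With day 1 as first dose, week w is day 7w + 1. So 7×56 + 1 = 393, 7×60 + 1 = 421, 7×64 + 1 = 449 and 7×68 + 1 = 477, as printed. These equal 365 + 28k for k = 1 to 4, which is week 52 plus 4, 8, 12 and 16 weeks. Each window opens at target − 14.

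**2. Derive the protocol days.** The last dose at week 50 is day 7×50 + 1 = 351, which agrees with the SAP's own Week 50 row. Follow-up visit k is planned for 351 + 28k.

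| Visit | Planned day (Table 2-2) | SAP target | SAP window opens | Target minus planned |
|---|---|---|---|---|
| 1 | 379 | 393 | 379 | 14 |
| 2 | 407 | 421 | 407 | 14 |
| 3 | 435 | 449 | 435 | 14 |
| 4 | 463 | 477 | 463 | 14 |

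**3. Follow an early visit through the rules.**
- Visit 1 may fall on days 374-384. Days 374-378 lie in the Week 52 window (vital signs 358-378, PK 337-378). They are 9-13 days from target 365, so an attended week 52 visit within 3 days of day 365 is kept and the follow-up record is left out of the by-visit summary.
- If the week 52 visit is missing, that record is reported as Week 52, although it was taken 23-27 days after the last dose and not 14 (365 − 351).
- An on-time visit 1 (day 379) is 14 days from target 393. If visit 2 then falls on days 402-406, it is only 9-13 days away and takes the Week 56 label instead.

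**4. Size.** Let e be the deviation of each visit from its 28-day interval, and S(k) the sum of the first k deviations. Visit k takes the previous label when S(k) < 0. The documents give no distribution for e, so three patterns are assumed and the sums are computed by exact convolution.

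| Assumed timing within ± 5 days | Visit 1 | Visit 2 | Visit 3 | Visit 4 | All four in own window |
|---|---|---|---|---|---|
| Uniform over the 11 days (visit 1: 5/11) | 45.5% | 45.5% | 46.6% | 47.0% | 31% |
| Half exactly on time, the rest uniform (visit 1: 0.5 × 5/11) | 22.7% | 34.1% | 39.9% | 43.0% | 46.5% |
| 20% early, 30% on time, 50% late | 20.0% | 24.0% | 23.2% | 21.5% | 61% |

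The last column is from a simulation of 400,000 subjects. The extremes are 0% if no visit is early and 100% if all are. Letting the last dose itself vary by ± 3 days barely moves the uniform case (45.4% to 46.9%).

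Applying the closest-to-target rule in the uniform case, with the week 52 visit at day 365 ± 3, 47.8% of follow-up records are kept under the right label, 32.8% are kept under a wrong label and 19.4% are left out.

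**5. Check the remedy.** With windows of 21-42, 43-70, 71-98 and at least 99 days since last dose, and uniform timing, visits 1-4 are correctly placed in 100%, 100%, 99.6% and 98.6% of cases. All four are right in 98% of subjects.

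**6. Check the Week 52 boundary.** If the week-50 dose is missed, the last dose is at week 48 (7×48 + 1 = day 337). Then 337 + 28 = 365, so the ordinary week 52 visit would sit on the target of the first follow-up window. The remedy therefore needs a precedence rule.

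**7. Hematology.** Follow-up samples are due at visits 2 and 4 (days 407 and 463). The Appendix D windows open on days 393 and 449, which leaves 14 days of margin.

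**The case against.** The strongest reply is that this is a labelling matter in a reduced SAP. After the futility stop, treatment comparisons were removed and only descriptive summaries remain. Appendix D selects records for by-visit summaries and deletes nothing, and protocol section 9.2.5 has the actual date and time of every PK sample recorded. The exact alignment holds only for subjects last dosed at week 50. Subjects still on treatment at termination were taken off drug before then, and the number who reached week 50 is not given. All of this stands, and it limits the consequence. It does not change the calendar arithmetic, and nothing else in the SAP corrects the windows.

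A reader might go further than the documents allow in four ways.
- That nearly half of follow-up visits are in fact mislabelled: this follows only if timing is spread about evenly over ± 5 days.
- That off-drug data are lost: they are left out of, or misplaced in, summary columns.
- That the mixing distorts concentrations greatly because drug levels fall steeply over four weeks: neither document states a half-life, and terminal half-life is itself an endpoint to be characterised.
- That hematology has the same fault: its windows still catch the planned visits.

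**Conclusion.** The vital-sign and PK follow-up windows in Appendix D are wrong as written for subjects last dosed at week 50. Each target is 14 days late, each window opens on the planned day, and any net-early visit within the permitted tolerance takes the previous label. That much follows from the documents alone.

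The share affected depends on visit timing that the documents do not report; the three assumed patterns give about 20% to 47% per visit. The effect is confined to descriptive vital-sign and serum-concentration summaries, which would mix different times since last dose after week 52. Efficacy endpoints, adverse event incidence and any half-life computed from actual sample times are not affected; the documents do not say how half-life is derived. The point is worth correcting because the rule is plainly misaligned and the repair is cheap. It does not threaten a trial conclusion.

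**What to change.** In Appendix D, assign vital-sign and PK follow-up records by days since the last dose of investigational product: targets 28, 56, 84 and 112 days, and windows of about 21-42, 43-70, 71-98 and 99 or more days. Label them 4, 8, 12 and 16 weeks after last dose.

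Apply these windows only to records after the subject's week 52 visit, or give the nominal week 52 visit precedence for the Week 52 label. Either rule keeps the day-365 visit in Week 52 when the week-50 dose is missed. Leave the hematology windows as they are.

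The cost is a change of SAP wording and one derived variable, days since last dose, from dates already collected. No visits, samples or subjects are added.

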Appendix E. Handling of Dates, Incomplete Dates and Missing Dates

The reference date for the following rules is the date of first dose rozibafusp alfa.

Start Date		Stop Date						Missing	
		Complete: yyyyymmdd		Partial: yyyyymm		Partial: yyyy			
		< 1 st dose	≥ 1 st dose	< 1 st dose yyyyymm	≥ 1 st dose yyyyymm	< 1 st dose yyyy	≥ 1 st dose yyyy		
Partial: yyyyymm	= 1 st dose yyyyymm	2	1	n/a	1	n/a	1	1	
	≠ 1 st dose yyyyymm		2	2	2	2	2	2	
Partial: yyyy	= 1 st dose yyyy	3	1	3	1	n/a	1	1	
	≠ 1 st dose yyyy		3		3	3	3	3	
Missing		4	1	4	1	4	1	1	

1=Impute the date of first dose or the randomization date if not treated; 2=Impute the first of the month;

3=Impute January 1 of the year; 4=Impute January 1 of the stop year

Note: For subjects who were never treated (first dose date is missing), partial start dates will be set to the first day of the partial month or first day of year if month is also missing.

Imputation Rules for Partial or Missing Stop Dates

Initial imputation

- If the month and year are present, impute the last day of that month.
- If only the year is present, impute December 31 of that year.
- If the stop date is entirely missing, assume the event or medication is ongoing.

If the imputed stop date is before the start date, set stop date to missing.

If the imputed stop date is after the death date, impute as death date.
